## 7.7 Serious AE Reporting

Serious AEs occurring after the patient has provided informed consent, but before the first dose of study treatment, will be collected as medical history unless the event is either new and attributed to protocol-mandated procedures by the Investigator or there is a significant change in the rate of occurrence or an increase in the severity of the pre-existing condition which is judged to be clinically important and attributed to the protocol-mandated procedures by the Investigator.

All SAEs, regardless of causality attribution, with an onset within 60 days after the last dose of study treatment (EOT), unless the patient withdraws consent to treat, initiates new anti-cancer therapy, is lost to follow up, or death occurs, will be reported to Nektar Therapeutics Drug Safety within **24 hours** after the site becomes aware of the event.

All AEs and SAEs will be recorded in the electronic case report form (eCRF) database within the timelines outlined in the eCRF completion guidelines. At the time of study start, SAEs may be reported using a paper SAE reporting form. During the study conduct, sites may transition to an electronic SAE (eSAE) system. Nektar or designee will provide training and account information prior to implementing an eSAE system at each site.

### 7.7.1 Electronic Serious Adverse Event (eSAE) Reporting Process

Site personnel record all SAE data in the eCRF database and from there transmit the SAE information to Nektar Drug Safety within 24 hours of the Investigator’s knowledge of the event. Detailed instructions can be found in the eCRF completion guidelines. If for any reason it is not possible to record the SAE information electronically, ie, the eCRF database is not functioning,

record the SAE on the paper SAE reporting form and submit within 24 hours of the Investigator's knowledge of the event to Nektar Therapeutics Drug Safety via email or Safety Fax as listed at the beginning of this protocol.

As soon as it is possible to do so, any SAE reported via paper must be transcribed into the eCRF database according to instructions in the eCRF completion guidelines. If an SAE has been reported via a paper form because the eCRF database has been locked, no further action is necessary.

For fatal or life-threatening events, copies of hospital case reports, autopsy reports, and other documents are also to be submitted by email or fax when requested and applicable. Transmission of such documents should occur without personal patient identification, maintaining the traceability of a document to the patient identifiers. Additional information may be requested to ensure the timely completion of accurate safety reports. Any medications necessary for treatment of the SAE must be recorded onto the concomitant medication section of the patient's eCRF and the event description section of the SAE form.

All SAEs will be followed as described in Section [7.8](#).

Reporting of SAEs to the IRB/IEC will be done in accordance with the standard operating procedures (SOPs) and policies of the IRB/IEC. Adequate documentation must be provided to Nektar Therapeutics, showing that the IRB/IEC was properly notified. Serious AEs will be reported by Nektar Therapeutics or designee to the Regulatory Authorities, per local regulations.

## **7.8 Serious AE Follow-up**

All study treatment-related SAEs that have not resolved within 60 days after the last dose of study treatment, until a new antineoplastic regimen has been initiated, loss to follow-up, withdrawal of consent, or death, will be followed until any of the following occurs (whichever comes first):

- The event resolves
- The event has stabilized
- The event returns to baseline, if a baseline value is available
- It is unlikely that any additional information can be obtained (eg, patient or health care practitioner refuses to provide additional information; lost to follow-up after demonstration of due diligence with follow-up efforts)
- The patient dies or is lost to follow-up

All ongoing SAEs assessed as "unrelated" to study drug(s) will be followed until resolution or until 60 days after the last dose of study treatment or until a new antineoplastic regimen has been initiated. In the case where an unrelated SAE has not completely resolved up to 60 days after the last dose of study treatment or until a new antineoplastic regimen has been initiated, the final

outcome of these ongoing SAEs will be captured as “Not Recovered/Not Resolved” or “Recovering/Resolving”, whichever is applicable.

### **7.9 Disease Progression and Death Due to Disease Progression – Not Reportable as an AE/SAE**

It is anticipated that during this study a proportion of patients will experience disease progression prior to study discontinuation. Disease progression should not be reported as an AE or SAE. In some patients disease progression may result in clinical manifestations (eg, pleural effusion) that meet “seriousness” criteria (eg, hospitalization). These clinical manifestations may be reported as non-fatal SAEs.

For all SAEs assessed as clinical manifestations associated with fatal disease progression, the following criteria will apply:

- Seriousness Criteria = Cannot equal to Death
- Severity = Cannot equal to Grade 5
- Outcome = Ongoing at time of Death

Deaths that are attributed by the Investigator solely to disease progression should not be reported as SAEs.

### **7.10 Pregnancy**

#### **7.10.1 Pregnancies in Female Patients**

The Sponsor must be notified within 24 hours of the initial report and any follow-up reports of a female study patient becoming pregnant during the course of the study **CCI**

via the Pregnancy

Notification Form for any pregnancy. The patient, once becoming aware of pregnancy, should reach out to the study Investigator for confirmation and consultation. In order for the Sponsor or designee to collect any pregnancy surveillance information, the pregnant patient will be asked to sign a Pregnancy Follow-up ICF. Pregnancy, although reportable, is not considered an AE/SAE unless a female patient experiences signs or symptoms of pregnancy complications (in which case the AE is the complication, not the pregnancy); however, the contact information for pregnancy reporting is the same as for SAE reporting and listed in Section 7.7 and the [List of Study Contacts](#). Female patients who become pregnant will be followed until the outcome of the pregnancy is known. Pregnancy follow-up should describe the outcome of the pregnancy, including any voluntary or spontaneous termination, details of the birth, and the presence or absence of any congenital abnormalities or birth defects in the offspring.

If a female patient becomes pregnant, administration of the study drug(s) must be discontinued immediately (Section 5.2.3.1, Section 5.2.3.2).

### 7.10.2 Pregnancies in Female Partners of Male Patients

The Sponsor must be notified within 24 hours of the initial report of a female partner of a male study patient becoming pregnant during the course of the study **CCI**

via the Pregnancy Notification Form. A female partner of the male patient will be asked to sign a Pregnancy ICF for follow-up of the pregnancy. The contact information for pregnancy reporting is the same as for SAE reporting and listed in Section 7.7 and the [List of Study Contacts](#). Attempts should be made to collect and report details of the course and outcome of any pregnancy in the partner of a male patient exposed to study drugs with the authorization from the pregnant partner. Pregnancy follow-up should describe the outcome of the pregnancy, including any voluntary or spontaneous termination, details of the birth, and the presence or absence of any congenital abnormalities or birth defects in the offspring.

### 7.11 Pregnancy Tests

[Appendix 7](#) describes acceptable methods of contraception. Patients must follow these guidelines while on study.

Serum pregnancy tests will be performed on WCBP during Screening, and serum or urine pregnancy test on Day 1 prior to each dose of study drug and at EOT. Serum pregnancy tests should have a minimum sensitivity of 25 IU/L or equivalent units of HCG. A negative pregnancy test result must be obtained before the administration of the study drug(s).

A pregnancy test does not need to be performed on women who are postmenopausal for at least 1 year or surgically sterile for at least 3 months before signing the ICF.

If a female patient becomes pregnant, administration of the study drug(s) must be discontinued immediately.

### 7.12 Clinical Laboratory Tests

Clinical laboratory tests will be conducted according to the Schedule of Events (Section 1.2). Clinical safety laboratory tests ([Appendix 4](#)) will be performed by a designated central laboratory. Central laboratory results must be used to determine patient eligibility, unless otherwise stated. In situations where central laboratory results are unavailable for eligibility determination, the Medical Monitor may approve of substitution of local laboratory results (a repeat full set of central laboratory results must be obtained prior to dosing). Clinical laboratory test data will be reviewed by the Investigator or Sub-Investigator. Additional clinical laboratory tests may be ordered at the Investigator's or qualified Sub-Investigator's discretion.

For treatment decisions at Cycle 2 and beyond, blood draw for the central laboratory may be obtained up to 5 days prior to the scheduled day of treatment. Depending on the turn-around time for the central laboratory, the results of these safety laboratory tests may not be available prior to the scheduled treatment. If the results are not available, or, at the discretion of the Investigator,

local laboratory results may be used to determine eligibility for retreatment. In all cases, if local laboratory results are used for retreatment decisions, duplicate central laboratory tests must be submitted to the central laboratory.

Treatment decisions require results for the following tests: hemoglobin, absolute neutrophil count (ANC), platelets, bicarbonate/carbon dioxide (CO2), calcium, chloride, potassium, sodium, and serum creatinine.

The Investigator or designee will review all laboratory results for clinical significance. Any laboratory result deemed clinically significant (ie, associated with signs and symptoms, requires treatment, or requires follow-up) will be recorded as an AE as described in Section 7.1.

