**Table 1: Schedule of Visits and Assessments – Phase 1b (CRC and HNSCC; NKTR-255 Dose Escalation) (Contd)**

Event a	Screening Period	Treatment Period																		Post-treatment Period				
		Run-in (1 week)			Cycle 1 (21-day cycle)						Cycle 2 (21-day cycle)						Cycle 3 (21-day cycle)			Cycle 4+ (21-day cycles)				
		Day	Day	Day	Day	Day	Day	Day	Day	Day	Day	Day	Day	Day	Day	Day	Day	Day	EOT b	60-day Follow-up c	Survival Follow-up c			
≤ 28d prior to Day 1 of Run-in Period	-7	-6	-4	1	2	3	4	5	8	10	15	1	2	3	4	8	10	15	1	4	8	15		
Windows (days)		+1			+1							+1						+1		+1		+7	±14	Every 3 months ±14 days
General and Safety Assessments																								
ECOG performance status	X	X			X						X						X		X		X		X	
Echocardiogram or MUGA or nuclear scan j	X																				X			
ECG k	X	X			X						X						X				X			
Adverse events review	Continuous from time of ICF until 60 days after last study treatment dose (refer to Sections 7.5 and 7.7)																							
Laboratory Assessments																								
Pregnancy test l	X	X			X						X						X		X		X		X	
Hematology m	X	X	X	X	X	X	X	X	X	X	X	X	X	X	X	X	X	X	X	X	X	X		
Serum chemistry m	X	X		X	X		X	X	X	X		X	X		X	X	X	X	X		X	X		
PT/PTT	X	X			X					X						X		X		X		X	X	
TSH, T4, lipase, amylase, CK n	X	X			X					X						X		X		X		X	X	
Urinalysis	X	X			X					X						X		X		X		X	X	

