- k. On C1D1 and C2D1, ECGs are required predose and end of NKTR-255 infusion. All other timepoints, collect ECGs predose. Patients must be resting quietly in the supine position for  $\geq$  5 minutes prior to collection of 12-lead ECG.
- l. For women of childbearing potential (WCBP) only, perform a serum beta subunit of human chorionic gonadotropin ( $\beta$ -HCG) pregnancy test at Screening within 10 to 14 days prior to dosing, and urine or serum pregnancy test within 24 hours prior to day of dosing NKTR-255 on C1D1. In subsequent cycles, perform urine or serum test once each dosing cycle. A negative result is required prior to dosing. Pregnancy testing is not required for women who are postmenopausal for at least 1 year, or surgically sterile for at least 3 months prior to signing the ICF.

- m. See [Appendix 4](#). Central safety laboratory results must be used to determine patient eligibility, with the exception that pregnancy tests are done locally (see Section 7.11); thereafter, central laboratory samples must be obtained prior to each cycle. If local laboratory results are used for retreatment decisions due to timing issues (eg, predose, treatment-related AE management, dose delays, etc.), duplicate central safety laboratory tests must be submitted to the central laboratory.
- n. Tests include free or total triiodothyronine (T3) reflex testing if TSH is abnormal.
- o. Refer to the Laboratory Manual for sample processing. See [Table 7](#) for detailed sampling timepoints.

- u. NKTR-255 will be administered q21d starting C1D1.
- v. Cetuximab will be administered at the recommended dose according to the current local prescribing information, ie, IV weekly. A loading dose of 400 mg/m^2 IV is given as an initial dose, then weekly doses of 250 mg/m^2 IV. On days that NKTR-255 and cetuximab are both dosed, cetuximab should be administered first, [CCI](#)
- w. Patients will remain on treatment until meeting one of the criteria for discontinuation of treatment in Section [5.2.3.1](#).

CCI

CCI

CCJ

CCI

CCI

CCI

CCI

CCI

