**APPENDIX 4: CLINICAL LABORATORY TESTS (ONLY TESTS DONE VIA CENTRAL LABORATORY)**

Clinical Laboratory Tests		
Hematology	Chemistry	Serology

 
• Hemoglobin (Hgb)
 
• Hematocrit (HCT)
 
• Red blood cell (RBC) count
 
• Platelet count
 
• White blood cell (WBC) count
 
• Neutrophils
 
• Lymphocytes
 
• Monocytes
 
• Eosinophils
 
• Basophils
 
• Mean corpuscular volume (MCV)
 
• Mean corpuscular hemoglobin (MCH)
 
• Mean corpuscular hemoglobin concentration (MCHC)
 
	
 
• AST (SGOT)
 
• ALT (SGPT)
 
• Alkaline phosphatase (ALP)
 
• Albumin
 
• Creatinine
 
• Calculated creatinine clearance
 
• Calcium
 
• Ferritin
 
• Gamma-glutamyl transferase (GGT)
 
• Glucose
 
• Total protein (TP)
 
• Total and direct bilirubin
 
• Sodium
 
• Potassium
 
• Chloride
 
• Magnesium
 
• Carbon dioxide (CO2) content or bicarbonate
 
• Blood urea nitrogen (BUN)
 
• Lactate dehydrogenase (LDH)
 
• Uric acid
 
	
 
• Hepatitis B surface antigen (HBsAg)
 
• Hepatitis B core antigens (anti-HBc)
 
• Hep B DNA
 
• Hepatitis C virus antibody (anti-HCV)
 
• Hepatitis C virus ribonucleic acid (HCV-RNA)
 
• Human immunodeficiency virus (HIV) antibody
 

Additional Labs		

 
• Creatine kinase (CK)
 
• Thyroid-stimulating hormone (TSH)
 
• Free thyroxine (free T4)
 
• Free or total triiodothyronine (T3)a
 
• Lipase
 
• Amylase
 
		
Coagulation		

 
• Partial thromboplastin time (PTT)
 
• Prothrombin time (PT)
 
• International normalized ratio (INR)
 
		
Urinalysis		

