
 
• Specific gravity
 
• pH
 
• Glucose
 
• Protein
 
• Bilirubin
 
• Ketones
 
• Leukocyte esterase
 
• Blood
 
	For positive protein, white blood cell or blood, a microscopic examination including: 
 
• Red blood cells
 
• White blood cells
 
• Epithelial cells
 
• Bacteria
 
• Crystals
 
• Casts
 
	
Minimal acceptable laboratory safety tests for local laboratory to assess suitability for retreatment of NKTR-255		
Hematology	Chemistry	

 
• Hemoglobin
 
• Platelet count
 
• Neutrophils including bands (absolute)
 
	
 
• Creatinine
 
• Sodium
 
• Potassium
 
• Chloride
 
• Calcium
 
• Bicarbonate/CO2
 
	

a. T3 should be tested in case of an abnormal TSH and normal T4. See the Laboratory Manual for further information.

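### The minimum laboratory set for NKTR-255 retreatment leaves out AST, ALT and total bilirubin, so a new liver rise may become known only after redosing

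*Protocol*

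**What the plan says.** Protocol 7.12 has a central laboratory run the safety tests. For Cycle 2 and beyond, the central draw "may be obtained up to 5 days prior to the scheduled day of treatment". The section accepts that, depending on turnaround, "the results of these safety laboratory tests may not be available prior to the scheduled treatment". In that case, or when the Investigator so chooses, "local laboratory results may be used to determine eligibility for retreatment". It then fixes the required set: "Treatment decisions require results for the following tests: hemoglobin, absolute neutrophil count (ANC), platelets, bicarbonate/carbon dioxide", followed by calcium, chloride, potassium, sodium and serum creatinine.

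Appendix 4 has a box headed "Minimal acceptable laboratory safety tests for local laboratory to assess suitability for retreatment of NKTR-255", with three hematology and six chemistry tests. The central chemistry panel in the same appendix does include AST, ALT and "Total and direct bilirubin".

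Table 1 schedules "Serum chemistry" at several visits within a cycle. Its footnote m requires a central sample to be obtained before each cycle. The same footnote covers the fallback: "If local laboratory results are used for retreatment decisions due to timing issues", a duplicate sample has to be sent to the central laboratory.

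**The concern.** The lists in 7.12 and Appendix 4 define what a site must know before it gives the next dose. Neither asks for a liver value. The text also describes the situation in which the liver value from the central panel will not be there. A site that runs the nine local tests, sends the central tube and doses has followed the protocol, yet has no current AST, ALT or bilirubin.

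At stake is re-exposure to NKTR-255 during a liver injury that would have stopped or delayed the dose had the result been read. The plan treats these tests as important elsewhere. Exclusion criterion 21 uses AST, ALT and bilirubin to bar entry. SAP 7.6.2 tracks raised hepatic transaminases as a safety observation, and SAP 7.6.4 plans a listing of Hy's law cases.

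**Working it through.** There is no plan figure to reproduce. The check is a count, a reading of which results must be back before dosing, a short calendar calculation, and a trace of the rules that act on liver values.

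**1. Count of tests.**

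| Test | 7.12 required results | Appendix 4 local box | Appendix 4 central panel |
|---|---|---|---|
| Hemoglobin, neutrophils, platelets | yes (3) | yes (3) | yes |
| Bicarbonate/CO2, calcium, chloride, potassium, sodium, creatinine | yes (6) | yes (6) | yes |
| AST, ALT, total bilirubin | no (0 of 3) | no (0 of 3) | yes (3 of 3) |
| Total of the tests above | 9 | 9 | 12 |

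The two minimum lists are the same nine tests.

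**2. Obtained or resulted?** Footnote m asks that the pre-cycle central sample be obtained. Both 7.12 and footnote m ask that a duplicate be submitted when local results are used. No visible text requires the central liver result to be back before the dose.

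**3. Age of the newest scheduled value.** The visit days in the Table 1 header run to Day 15 at the latest in every cycle. With dosing every 21 days, the next dose falls on Day 1 + 21 = Day 22.

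- On schedule: 22 − 15 = 7 days.
- With the +1-day window on Day 1: 23 − 15 = 8 days.
- If the central draw is taken the full 5 days early and is back in time: 5 days.

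The columns of Table 1 are broken in the text available, so the chemistry marks cannot be matched to days with certainty. That does not affect the lower bound: no visit day is later than Day 15, so a mid-cycle value cannot be newer than 7 days at Day 22. The calculation does not cover 28-day maintenance, whose schedule is not visible.

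**4. Which rules act on the missing value.**

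| Finding not yet known at redosing | Visible rule | What is lost |
|---|---|---|
| Grade 4 hepatic abnormality | 5.7 requires permanent discontinuation for any Grade 4 laboratory abnormality outside a short list of exceptions, none hepatic; 5.3.1.5 does so for Grade 4 non-hematological toxicity with no other identifiable cause | A mandatory stop |
| Grade 3 hepatic toxicity | 5.3.1.5 permits withholding if it cannot be managed medically | An option to hold |
| Any abnormality the Investigator would judge a substantial risk | 5.7 requires discontinuation | A stop that depends on the Investigator seeing the value |
| Combined Grade 2 AST/ALT and bilirubin | 5.3.1.6 directs discontinuation by reference to parameters in 5.7 | Possibly a stop; no combined hepatic parameter is visible in 5.7 |
| Isolated Grade 1–2 rise | 5.3.1.5 requires no delay or reduction | Nothing mandatory |

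**The case against.** The strongest objection is the redaction. Section 5.11 is blacked out. By the table of contents it lies between 5.10.3, which starts on page 93, and 5.12, which starts on page 100. Section 5.7 cites it for the criteria for continued treatment. It may already require liver results before each dose, in which case only a cross-reference is missing. This stands as a real limit. It does not change what the two visible lists present as the required and minimum set, and neither refers to 5.11.

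The second objection is that safeguards already make the case rare. Chemistry is scheduled several times per cycle, a central sample precedes every cycle, the draw may be taken early so that results return, and extra tests are allowed. The Appendix 4 list is a floor, and a patient already held for a hepatic AE must show resolution under 5.3.1.6. All of this is correct and makes the gap narrow. But the early draw and the extra tests are optional, the pre-cycle sample need not be resulted, and the resume criteria act only on an abnormality already known.

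The third objection concerns consequences. Three of the nine DLT examples in 5.5.1 (Hy's law, Grade 3 or higher AST/ALT, Grade 3 or higher bilirubin) rest on these tests. A reader might infer that redosing would breach a DLT stopping rule or cause DLTs to be missed. The documents do not support that. Section 5.7 does not list a DLT as a reason to discontinue, and a Grade 3 toxicity only permits a hold. The central sample is still drawn and read, so DLT ascertainment and Safety Review Committee review are unaffected. Nor can one say that the combined AST/ALT–bilirubin rule would be broken: it sits among the resume criteria, and the 5.7 parameters it cites are not visible.

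**Conclusion.** The point holds as a narrow safety-monitoring gap. On the visible text, a compliant site can redose from Cycle 2 on with none of the three liver results current. The newest scheduled mid-cycle value is then at least 7 days old on the 21-day schedule. The clear consequences are a missed mandatory stop at Grade 4, a missed option to hold at Grade 3, and a missed substantial-risk stop by the Investigator.

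This rests on four conditions occurring together: the rise is new and asymptomatic, it follows the last resulted chemistry, the pre-cycle central result is outstanding, and no extra local test was ordered. The documents give no rate for late central results or for hepatic events, so no frequency can be stated. The listing of raised transaminases in the SAP shows that they are monitored; it does not show how often they occur.

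Severity is minor to moderate, as a cheap improvement. Confidence is limited by the redaction of Section 5.11.

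**What to change.** In both Protocol 7.12 and the Appendix 4 local box, add AST, ALT and total bilirubin, from either the central or the local laboratory, to the results that must be available before each NKTR-255 dose from Cycle 2 on. The minimum set goes from 9 to 9 + 3 = 12 tests. If Section 5.11 already requires this, put a cross-reference to it in both places instead. Leave the action thresholds in the clinical sections as they are.

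The cost is wording in two places and three more analytes on a chemistry sample that is already drawn, with no new visit or procedure. Section 5.5.1 already expects the local laboratory to reconfirm laboratory DLT findings within 24 hours, so local liver testing is already assumed. The downside is an occasional short wait for a result before dosing.
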